#### 8.4.2 Safety Endpoints

The primary safety objective of this trial is to characterize the safety and tolerability of pembrolizumab in subjects with head and neck cancer. The primary safety analysis will be based on subjects who experienced toxicities as defined by CTCAE Version 4.0 criteria. Safety will be assessed by quantifying the toxicities and grades experienced by subjects who have received pembrolizumab, including serious adverse events (SAEs) and events of clinical interest (ECIs).

Safety will be assessed by reported adverse experiences using CTCAE, Version 4.0. The attribution to drug, time-of-onset, duration of the event, its resolution, and any concomitant medications administered will be recorded. AEs will be analyzed including but not limited to all AEs, SAEs, fatal AEs, and laboratory changes. Furthermore, specific immune-related adverse events (irAEs) will be collected and designated as immune-related events of clinical interest (ECIs) as described in Section 7.2.3.2.

Consider referring to Section 4.2.3 for the initial description of safety measures.

#### 8.4.2.1 Analysis Populations

#### 8.4.2.2 Efficacy Analysis Populations

The Full Analysis Set (FAS) population will serve as the primary population for the analysis of efficacy data in this study. The FAS population consists of all subjects who:

- Receive at least one dose of study treatment,
- Complete the treatment end imaging study

A supportive analysis using the All Patients as Treated (APaT) population, defined as all enrolled subjects who receive at least one dose of study medication, will be performed for the primary efficacy endpoint(s). Supportive analyses in the FAS population using the site radiology assessment will require baseline scan with measureable disease per RECIST 1.1 using site radiology assessment.

Patients who undergo surgical resection prior to treatment end imaging will be included in the efficacy analysis. These patients will be determined as having PD.

Details on the approach to handling missing data are provided in Section 8.6 Statistical Methods.

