13. Patients with residual disease (SD, PR, or PD) on post-treatment imaging will undergo salvage surgical resection (at the discretion of the surgeon) if their disease is felt curable with salvage surgery. Additionally, patients with a CR and clinical suspicion for viable residual disease will be offered salvage surgery. Following pathology analysis, salvage surgical tissue will be sent for correlative studies. Detailed instructions for tissue collection, processing, and shipment are included in the procedures manual.

14. PET imaging at baseline and treatment end is not required for the study, but is allowed for use to determine complete response rate when tumor response on standard imaging cannot confirm CR based on RECIST 1.1. Please see sections 7.1.2.6.2 and 7.1.2.6.3 for details.

15. Screening labs completed within 7 days (168 hours) of treatment initiation (day -7) will not need to be repeated.

16. Once a subject experiences confirmed disease progression or starts a new anti-cancer therapy, the subject moves into the Survival Follow-Up Phase. These subjects will be followed every 6 months to assess for survival status until death, withdrawal of consent, or the end of the study, whichever occurs first.

17. If a subject discontinues pembrolizumab, return visit timing is left to treating physician discretion until day 150 although it is highly recommended that the subject return for Day 78, 120, and 150 so research specimens and QOL can be collected.

18. Minimum interval between pembrolizumab doses is 14 days.

19. Vital signs and weight do not need to occur on the same day as the visit but need to be completed within the window and prior to the next treatment.

20. Once a subject transitions to follow-up all documented AEs will be followed until resolution or to a new baseline as determined by the treating investigator. Only new AEs that could be considered an ECI or irAR will be documented and followed while in follow-up.

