#### 7.1.4 **Other Procedures**

#### 7.1.4.1 Withdrawal/Discontinuation

When a subject discontinues/withdraws prior to active trial completion, the subject will need to sign a withdrawal consent. If the subject becomes cognitively impaired while on this study the subject and/or their Legal Representative will have the opportunity to sign a withdrawal consent. All applicable activities scheduled for the final trial visit should be performed at the time of discontinuation/withdrawal. Any adverse events which are present at the time of discontinuation/withdrawal should be followed in accordance with the safety requirements outlined in Section 7.2 - Assessing and Recording Adverse Events. After discontinuing treatment following completion, subjects should return to the site for a Safety Follow-up Visit (described in Section 7.1.5.) and then proceed to the Follow-Up Period of the study (described in Section 7.1.5.4).

Subjects will have the option to withdraw from the study completely or partially which will allow following for progression/survival.

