#### 8.4 Analysis Endpoints

#### 8.4.1 **Efficacy Endpoints**

Radiographic Complete response (rCR) rate: proportion of subjects in the analysis population who have a complete response on RECIST 1.1 imaging at treatment end.

PET NPV rate: proportion of subjects in the analysis population who are considered to have NPV based on Hopkins Criteria scoring at treatment end.

Pathologic complete response (pCR) rate: proportion of subjects in the analysis population who have stable disease (SD) or partial response (PR) on RECIST 1.1 imaging at treatment end, who undergo salvage surgical resection and have a complete response determined on histologic evaluation.

Overall Complete Response (CR) rate: this is a composite proportion of subjects in the analysis population with a rCR, PET NPV, and pCR. This is the primary measure of efficacy for the study.

Overall Response Rate (ORR): proportion of subjects in the analysis population who have complete response (CR) or partial response (PR) based on RECIST 1.1 imaging at treatment end.

Progression-Free Survival (PFS): time from Day -7 treatment administration to the first documented disease progression or death.

Overall Survival (OS): time from Day -7 treatment administration to death due to any cause.

Locoregional Control (LRC): time from day -7 treatment to date of local or regional relapse within the primary radiation treatment field (relapse in the head or neck region, excluding CNS recurrence).

Rate of Distant Metastases (DM): proportion of subjects in the analysis population who develop distant recurrence, as defined by recurrence outside of the primary radiation treatment field (head and neck region).

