#### 8.4.3 Statistical Methods

#### 8.4.3.1 Statistical Methods for Efficacy Analyses

The efficacy endpoints, analysis population, and statistical methods (including missing data handling) that will be employed for the efficacy analyses are presented in Table 7.

The primary endpoint is the total CR rate (composite outcome of rCR, PET NPV, and pCR) on all subjects. We have designed the study to test the hypothesis that the CR rate will be greater than 40.2% assuming a rate of 60.4%. To test this, we will use a one sample, one-sided asymptotic equality test with the null hypothesis that the total CR rate will be 40.2%. This test will result in a p-value greater than 0.05 if fewer than 21 patients respond to treatment. Secondary endpoints will include rCR, pCR, PET NPV, PFS, OS, LRC, and DM rates. For the secondary endpoints, we will only estimate confidence intervals to understand the possible range of values rather than doing formal hypothesis testing. Survival curves for PFS and OS will be constructed using the Kaplan-Meier method and 1 and 2-year survival estimates will be calculated.

Endpoint Statistical Method		Analysis Population	Missing data approach			
rCR Rate	Exact binomial method: Clopper-Pearson 95% confidence interval	FAS	Subjects with missing data are considered non-responders			
pCR Rate	Exact binomial method: Clopper-Pearson 95% confidence interval	FAS 	Subjects with missing data are considered non-responders			
CR Rate	One sample, one-sided asymptotic binomial test	FAS	Subjects with missing data are considered non-responders			
Objective Response Rate (CR + PR)	Exact binomial method: Clopper-Pearson 95% confidence interval	FAS	Subjects with missing data are considered non-responders			
PFS (RECIST 1.1) by independent radiology review	Summary statistics using Kaplan-Meier method	ASaT	Censored at last assessment date			
OS	Summary statistics using Kaplan-Meier method	ASaT	Censored at last assessment date			
LRC rate	Exact binomial method: Clopper-Pearson 95% confidence interval	FAS	Subjects with missing data are considered as disease not under control			
DM rate Exact binomial method: Clopper-Pearson 95% confidence interval		FAS	Subjects with missing data are considered as disease not under control			

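### The primary efficacy set requires a completed treatment-end scan, so the rule that counts missing data as non-response cannot reach treated patients who were never scanned

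*Combined protocol and SAP*

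**What the plan says.** Section 8.4.2.2 makes the FAS primary for efficacy. Membership needs two things: having been dosed, and "Complete the treatment end imaging study". One exception is stated: "Patients who undergo surgical resection prior to treatment end imaging will be included in the efficacy analysis", scored as progressive disease (also Section 7.1.2.6.3.4). The same section plans "A supportive analysis using the All Patients as Treated (APaT) population" for the primary endpoint; that set needs only one dose.

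Table 7 (Section 8.4.3.1) assigns the CR rate to the FAS, with the method "One sample, one-sided asymptotic binomial test" and the missing-data rule "Subjects with missing data are considered non-responders". The text above the table says the primary CR rate is taken on all subjects. Section 8.4.1 defines the endpoint: "this is a composite proportion of subjects in the analysis population with a rCR, PET NPV, and pCR".

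On getting the scan, flow chart note 17 says of patients who stop pembrolizumab that "it is highly recommended that the subject return for Day 78, 120, and 150". Section 7.1.4.1 says "All applicable activities scheduled for the final trial visit should be performed at the time of discontinuation/withdrawal". Section 7.1.2.6.2 leaves imaging at clinical progression to clinical judgement.

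**The concern.** A rule that scores missing outcomes as failures protects against patients who do badly and are never assessed. Here the set to which it applies is defined by having been assessed, so the patients who most need the rule are removed before it operates. Death, full withdrawal, loss to follow-up, or clinical deterioration without imaging before about day 150 would each take a patient out of both numerator and denominator. A patient who goes to early surgery counts as a failure; one who dies before the scan does not count at all.

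The headline CR rate, and any decision to proceed to a phase III trial, would then describe scan completers and not the patients treated. In cohorts of 34 and 23, a few such patients matter.

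**Working it through.** **1. Whom the rule reaches**

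| Treated patient | In FAS? | Scored as |
|---|---|---|
| Scan done and readable | Yes | As read |
| Scan done, but read unevaluable or PET/pathology missing | Yes | Non-responder (Table 7), unless CR is met by another component |
| Resected before the scan | Yes (stated exception) | Progressive disease |
| No scan and no early surgery | No | Not counted |

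The rule works in the second row. The fourth row is the gap. In the APaT set, the Section 8.4.1 definition would put those patients in the denominator as non-CR, but that analysis is only supportive and no missing-data rule is written for it.

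**2. The plan's own figures**

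Section 8.4.7.3 gives at least 31/34 CRs against 74% (HPV-positive) and at least 18/23 against 50% (HPV-negative), each said to have type I error 0.05 and power 80%. The exact upper tail is P(X ≥ r | n, p).

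- HPV-positive: P(X ≥ 31 | 34, 0.74) = 0.012; power at 0.90 = 0.554.
- HPV-negative: P(X ≥ 18 | 23, 0.50) = 0.005; power at 0.75 = 0.468.

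The stated 0.05 and 80% are not reproduced. That is a separate matter; the exact values serve as the baseline below.

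**3. A result at the cut-off, with m further treated patients unscanned and counted as non-CR**

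m is an assumption. The p-value is P(X ≥ r | n+m, p0).

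| Cohort | m=0 | m=1 | m=2 | m=3 | m=4 |
|---|---|---|---|---|---|
| HPV-positive, 31/(34+m) | 91.2%, p=0.012 | 88.6%, p=0.031 | 86.1%, p=0.065 | 83.8%, p=0.118 | 81.6%, p=0.191 |
| HPV-negative, 18/(23+m) | 78.3%, p=0.005 | 75.0%, p=0.011 | 72.0%, p=0.022 | 69.2%, p=0.038 | 66.7%, p=0.061 |

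Two HPV-positive or four HPV-negative patients take a result at the cut-off past 0.05.

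**4. False success under the count rules**

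Assume that the all-treated CR rate equals the null, a fraction d is unscanned, all of those are non-CR, accrual continues to 34 and 23 scanned patients (Section 8.4.7.1), and the benchmark study lost nobody. The rate among scanned patients is then p0/(1−d).

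| d | HPV-positive, P(X ≥ 31 of 34) | HPV-negative, P(X ≥ 18 of 23) |
|---|---|---|
| 0 | 1.2% | 0.5% |
| 5% | 3.9% | 1.1% |
| 10% | 12.2% | 2.1% |
| 15% | 34.2% | 4.3% |

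HPV-positive reaches 5.0% at d=6%. If unscanned patients have half the null CR rate, the scanned rate is 0.74(1−d/2)/(1−d), and HPV-positive false success is 2.2% at d=5% and 4.2% at d=10%. If the benchmark lost patients to the same extent, the scanned rate under the null stays 74% and the figure stays 1.2%. If accrual stops at 34 enrolled, dropping non-CR patients adds no CRs, so it cannot exceed 1.2%.

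**5. Pooled test against 40.2% (Section 8.4.3.1)**

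z = (x/n − p0)/√(p0(1−p0)/n). At the planned rate, 57 × 0.604 ≈ 34 CRs. On all 57, 34/57 gives z=2.99, p=0.001. With five unscanned non-CR patients removed, 34/52 gives z=3.70, p=0.0001. The conclusion is the same.

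**The case against.** The strongest reply is that the FAS matches its comparator. Both nulls, 20/27 and 6/12, are rates among evaluable patients (Sections 4.2.3.5 and 8.4.7.3), so testing scan completers against them is like for like, while an all-treated rate is tested against a null that is too high for it. This stands as a reason to keep the FAS analysis and to call the all-treated test conservative. It does not make the FAS rate an estimate for treated patients, and nothing shows that loss in the benchmark study resembles loss here.

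Second, much is already handled: early surgery counts as failure, the APaT analysis is prespecified, and progression as a reason for discontinuation has to be radiographically confirmed (Section 5.9). This narrows the group but does not empty it. Replacement under Section 5.10 does not cover patients who stop for adverse events or progression, and does not return an unscanned patient to the denominator.

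Third, Sections 8.1 and 8.2 point to further SAP detail that is not in the text reviewed and might address this. The text available is nevertheless explicit.

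A reader might go further and infer that a single unscanned patient can overturn the trial's result. For example, 29/33 gives p=0.035 and 29/34 gives p=0.067 with the asymptotic test against 74%. The documents do not support that inference. Where the asymptotic test is written out, its null is the pooled 40.2%; the 74% and 50% nulls come with count rules, and 29 CRs miss the cut-off of 31 under either denominator.

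**Conclusion.** The point holds as a structural one: the set definition disables the missing-data rule for treated patients with neither a scan nor early surgery, and it conflicts with the statement that the endpoint covers all subjects. The rule is not wholly empty, since it still acts on scanned patients with incomplete results.

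The headline CR rate is biased upward for treated patients if unscanned patients are less often CR. That is plausible but not documented, and the size cannot be computed without a missing-scan rate. The two-patient and four-patient illustrations assume results exactly at the cut-offs and no CR among the unscanned.

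A reader might also infer that the trial's type I error is inflated. The documents do not establish that. It requires both accrual to 34 and 23 scanned patients and greater loss than in the benchmark study. They do not settle the first, because Section 5.1.1 counts enrolled patients while Sections 8.1 and 8.4.7.1 count evaluable ones, and they are silent on the second. Even with both conditions met and every unscanned patient non-CR, HPV-negative stays at or below 4.3% up to 15% unscanned. The pooled test is not materially affected.

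**What to change.** By protocol amendment, which Section 8.2 requires for a change to methods for a primary hypothesis:

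- Make the APaT set primary for the CR rate and state that no treatment-end assessment counts as non-CR. Keep treated patients who were replaced under Section 5.10 in the denominator.
- Keep the scan-completed FAS as the supportive analysis that is like for like with the 20/27 and 6/12 benchmarks, and say that the all-treated test against those nulls is conservative. Recounting the benchmark on all treated patients would remove the mismatch if those data can be had.
- Where the treated denominator differs from 34 or 23, recompute the cut-off for the actual n at one-sided 0.05. For example, n=36 needs 32 CRs (exact p=0.025) and n=27 needs 19 (p=0.026). The same criterion gives 30 at n=34 and 16 at n=23, so the basis of the present 31 and 18 should be settled at the same time.
- Report unscanned patients with reasons, by HPV cohort. Reconcile enrolled with evaluable across Sections 5.1.1, 8.1 and 8.4.7.1. Correct the pointer to Section 8.6, which is not in the document.

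Both analyses are already planned and no new data are needed. The costs are an amendment made after 27 patients were enrolled and early open-label responses were seen, a somewhat lower headline rate, and less power. If 90% and 75% are rates among scanned patients, exact power P(X ≥ r | n, p1(1−d)) at 31/34 is 55%, 25% and 9% with 0, 5% and 10% unscanned; at 18/23 it is 47%, 31% and 19%. If they are all-treated rates, power stays at 55% and 47%.

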#### 8.4.2.3 Safety Analysis Populations

The All Subjects as Treated (ASaT) population will be used for the analysis of safety data in this study.

At least one laboratory or vital sign measurement obtained subsequent to at least one dose of study treatment is required for inclusion in the analysis of each specific parameter. To assess change from baseline, a baseline measurement is also required.

#### 8.4.3 Statistical Methods

#### 8.4.3.1 Statistical Methods for Efficacy Analyses

The efficacy endpoints, analysis population, and statistical methods (including missing data handling) that will be employed for the efficacy analyses are presented in Table 7.

The primary endpoint is the total CR rate (composite outcome of rCR, PET NPV, and pCR) on all subjects. We have designed the study to test the hypothesis that the CR rate will be greater than 40.2% assuming a rate of 60.4%. To test this, we will use a one sample, one-sided asymptotic equality test with the null hypothesis that the total CR rate will be 40.2%. This test will result in a p-value greater than 0.05 if fewer than 21 patients respond to treatment. Secondary endpoints will include rCR, pCR, PET NPV, PFS, OS, LRC, and DM rates. For the secondary endpoints, we will only estimate confidence intervals to understand the possible range of values rather than doing formal hypothesis testing. Survival curves for PFS and OS will be constructed using the Kaplan-Meier method and 1 and 2-year survival estimates will be calculated.

Endpoint Statistical Method		Analysis Population	Missing data approach			
rCR Rate	Exact binomial method: Clopper-Pearson 95% confidence interval	FAS	Subjects with missing data are considered non-responders			
pCR Rate	Exact binomial method: Clopper-Pearson 95% confidence interval	FAS 	Subjects with missing data are considered non-responders			
CR Rate	One sample, one-sided asymptotic binomial test	FAS	Subjects with missing data are considered non-responders			
Objective Response Rate (CR + PR)	Exact binomial method: Clopper-Pearson 95% confidence interval	FAS	Subjects with missing data are considered non-responders			
PFS (RECIST 1.1) by independent radiology review	Summary statistics using Kaplan-Meier method	ASaT	Censored at last assessment date			
OS	Summary statistics using Kaplan-Meier method	ASaT	Censored at last assessment date			
LRC rate	Exact binomial method: Clopper-Pearson 95% confidence interval	FAS	Subjects with missing data are considered as disease not under control			
DM rate Exact binomial method: Clopper-Pearson 95% confidence interval		FAS	Subjects with missing data are considered as disease not under control			

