## 8.4.7.3 Sample Size and Power Calculations

Sample size for this study will be powered based on the co-primary outcome of efficacy. Efficacy will be defined by the rCR rate at the treatment end imaging evaluation. The rCR rate will be defined by RECIST 1.1 criteria. Based on the Intergroup Trial evaluating the gold standard of high-dose bolus cisplatin 100 mg/m2 given on days 1, 22, and 43 of radiation at 70 cGy, the complete response rate was 40.2% [10]. This study included both HPV+ and HPV-patients with unresectable disease and did not differentiate response based on HPV status. Extrapolating on our data from the animal model, we anticipate at least a 50% improvement in this CR rate. Therefore, we estimated a CR rate of 60.4% with this study regimen in all-comers.

For the initial sample size calculation, Simon's two-stage design with the Minimax approach was utilized. The null hypothesis that the true response rate is 0.402 will be tested against a one-sided alternative. In the first stage, 27 patients were to be accrued. If there are 13 or fewer CRs in these 27 patients, the study will be stopped. Otherwise, 12 additional patients will be accrued for a total of 39. The null hypothesis will be rejected if 21 or more CRs are observed in 39 patients. This design yielded a type I error rate of 0.05 and power of 0.80 when the true CR rate is 0.604.

At the time of interim analysis, 27 patients are enrolled in the study. During this analysis, an internal analysis of a similar study (NCT01386632) using standard of care high-dose cisplatin

(100 mg/m2 on days 1, 22, and 43) in a similar cohort of patients was performed. Distinct differences in response were seen in the HPV+ and HPV- groups, which mirror efficacy findings in similar studies. This analysis has revealed that 20 of 27 (74%) of evaluable patients with HPV positive disease achieved a CR (based on 3-month post-radiation CT and/or PET or subsequent salvage surgery).

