Based on this new data, we have reassessed our power calculations for our HPV positive cohort, With this novel combination therapy we estimate that an improvement in efficacy of >20% to a CR rate of 90% would warrant future study of this regimen in HPV positive disease. Therefore, using a one-arm binomial design the null hypothesis that the true response rate is 74% will be tested against a one-sided alternative. The null hypothesis will be rejected if 31 or more CRs are observed in 34 patients. This design yields a type I error rate of 0.05 and power of 80% when the true response rate is 90%.

Reviewing the same data, the HPV negative cohort had 6 of 12 (50%) evaluable patients achieving a CR (based on 3-month post-radiation CT and/or PET or subsequent salvage surgery). Therefore, reassessing our power calculations for the HPV negative cohort in the proposed expansion cohort, we estimate a CR rate of 75% (50% improvement from the standard of care) with the study regimen would warrant future study of this regimen in HPV negative disease. Therefore, using a one-arm binomial sample size, the null hypothesis with a true response rate of 50% will be tested against a one-sided alternative. The null hypothesis will be rejected if 18 or more responses are observed in 23 patients. This design yields a type I error rate of 0.05 and power of 80% when the true response rate is 75%.

At the time of the interim analysis, 20 patients with HPV + disease are enrolled and 7 patients with HPV - disease are enrolled. Based on this reanalysis of sample size and power calculations, an additional 14 HPV positive patients and 16 HPV negative patients would need to be enrolled after the interim analysis.

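### Section 8.4.3.1 still makes the primary efficacy test a pooled test against 40.2%, although the redesign implies separate tests by HPV cohort

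*Combined protocol and SAP*

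**What the plan says.** Section 8.4.3.1 names the composite CR rate over all subjects as primary, with a design null of 40.2% and an assumed rate of 60.4%. The test is a one-sample, one-sided "asymptotic equality test with the null hypothesis that the total CR rate will be 40.2" per cent. It adds: "This test will result in a p-value greater than 0.05 if fewer than 21 patients respond to treatment". The CR row of Table 7 gives "One sample, one-sided asymptotic binomial test" and does not say whether it is pooled or by cohort. Neither place mentions 74%, 50%, 31/34 or 18/23.

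Section 8.4.7.3 describes the 40.2% design as the initial calculation, a Simon "two-stage design with the Minimax approach was utilized", with the final rule "The null hypothesis will be rejected if 21 or more CRs are observed in 39 patients". It continues that "we have reassessed our power calculations for our HPV positive cohort", sets the HPV-positive null at 74% and states "The null hypothesis will be rejected if 31 or more CRs are observed in 34 patients". The HPV-negative null is 50%, rejected at 18 of 23. Each cohort rule is said to have type I error 0.05 and 80% power (at 90% and 75%).

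Other sections fit the cohort reading. Section 3.1 gives HPV-specific CR targets, 4.2.3.5 proposes separate evaluation, 5.1.1 and 5.5 fix cohorts of 34 and 23, and 8.4.7.1 continues accrual to those numbers. Some do not fit: 8.1 describes estimation without a hypothesis, 8.4.7 still has a total of 39, and 8.4.7.4 lists HPV status only as a subgroup factor. The endpoint also varies. It is the composite in 8.4.1 and 8.4.3.1, rCR plus pCR in 8.4.7.1, and in 8.4.7.3 "Efficacy will be defined by the rCR rate at the treatment end imaging evaluation".

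**The concern.** The sample-size section was rewritten for the redesign and the analysis section was not. An analyst who follows 8.4.3.1 runs one pooled test; one who follows 8.4.7.3 runs two cohort tests. The two can disagree about whether the trial succeeded, because 40.2% is well below the sponsor's own control rates by HPV status (20/27 and 6/12). The trial is open-label, and 4.2.3.5 already reports CRs in 8 of 8 imaged HPV-positive patients, so the primary decision rule should not need interpretation once results are in.

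**Working it through.** **Inputs.** p0 = 0.402 and p1 = 0.604 (8.4.3.1); 27 then 39 patients with limits 13 and 21, HPV-positive n = 34 (0.74 vs 0.90, reject at 31) and HPV-negative n = 23 (0.50 vs 0.75, reject at 18) (8.4.7.3); total 57 (1.0, 2.1).

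**1. The plan's figure reproduces for 39 patients.** The exact two-stage sum for 13/27 then 21/39 gives alpha 0.0498 and power 0.801, as stated. For the test in 8.4.3.1, z = (x/n − p0)/√(p0(1 − p0)/n). At n = 39 the standard error is √(0.402 × 0.598/39) = 0.0785:
- 20/39: z = 1.41, p = 0.079
- 21/39: z = 1.74, p = 0.041

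So 21 is the n = 39 boundary.

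**2. The same test at 57.** The standard error is √(0.402 × 0.598/57) = 0.0649:
- 21/57 (36.8%, below the null): p = 0.70
- 29/57: p = 0.0501
- 30/57: p = 0.028

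The boundary is 30.

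**3. The conclusion can reverse.** 25/34 = 73.5% is below 74%, and 11/23 = 47.8% is below 50%. Pooled, 36/57 = 63.2%, z = 3.535, p = 0.0002. The largest total with both cohort rules failing is 30 + 17 = 47, so totals from 30 to 47 can be significant pooled while neither cohort passes.

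**4. How often.** P(X + Y ≥ 30), with X ~ Bin(34, a) and Y ~ Bin(23, b), without the interim futility rule:

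| Assumed true rates (HPV+/HPV−) | Pooled test rejects |
|---|---|
| 74% / 50% | 97.8% |
| 70% / 45% | 90% |
| 65% / 40% | 69% |
| 60% / 40% | 51% |
| 54% / 21% | 4% |

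At 74%/50%, 96.1% of trials reject pooled with neither 31/34 nor 18/23 met. The expected pooled rate is (34 × 0.74 + 23 × 0.50)/57 = 64.3%. The range is wide because the controls are small: exact 95% intervals are 54–89% for 20/27 and 21–79% for 6/12.

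**5. Table 7 applied by cohort.** The same z formula with each cohort's null gives:
- HPV-positive: 29/34 p = 0.067; 30/34 p = 0.029; 31/34 p = 0.011
- HPV-negative: 15/23 p = 0.072; 16/23 p = 0.030; 17/23 p = 0.011; 18/23 p = 0.003

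Thus 30/34, 16/23 and 17/23 are significant at 0.05 but miss the printed counts. At the design rates these results occur with probability P(X = 30 | 34, 0.90) = 19.7% and P(16 ≤ X ≤ 17 | 23, 0.75) = 33.5%.

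**6. Exact alpha and power of the cohort rules.**

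| Rule | Alpha | Power |
|---|---|---|
| 31/34 (printed) | 1.2% | 55% |
| 30/34 | 3.8% | 75% |
| 18/23 (printed) | 0.5% | 47% |
| 16/23 | 4.7% | 80% |

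Neither printed count has the stated 0.05 and 80%. No count at n = 34 has both, since 29/34 has alpha 9.1%.

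**The case against.** The strongest reply is that the plan, read as a whole, has already replaced the pooled test. Section 8.4.7.3 calls it initial, reports it in the past tense and says power was reassessed; 4.2.3.5 says efficacy will be evaluated separately; 3.1 and 5.1.1 are written by HPV status. On that view this is one stale paragraph and a leftover 39. Most of this stands: supersession is strongly implied. But those words concern sample size and intent, and none withdraws or demotes the only formal efficacy test in the methods section. A separate SAP, to which 8.1 refers, might settle it, but 8.4.3.1 would still have to agree.

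A reader might infer three stronger things that the documents do not support:
- **That the pooled test is an equal option for the sponsor to pick after the data.** The weight of the text is against this.
- **That 97.8% is a false-positive rate.** It is not: at 74%/50% the pooled rate is 64.3%, so rejecting 40.2% is correct. The figure also depends on 27 and 12 control patients.
- **That 21 of 57 would count as success.** Section 8.4.3.1 says only that fewer than 21 is not significant, which remains true at 57 but is no longer the boundary.

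**Conclusion.** The point holds as a textual conflict in the primary analysis and should be corrected before analysis. Section 8.4.3.1 is pre-redesign text, shown by a count that fits only 39 patients, and the pooled test is never withdrawn. The reversal at 25/34 and 11/23 needs no assumption about true rates. The 97.8% assumes 74%/50% and falls to 4% at 54%/21%; its use is to show that a 40.2% benchmark cannot stand in for the cohort nulls. Reading Table 7 by cohort does not resolve the conflict, because its p-values and the 8.4.7.3 counts disagree at 30/34, 16/23 and 17/23. The mismatch between the printed cut-offs and their stated 0.05/80% is a separate defect, to be settled before those cut-offs are carried into 8.4.3.1. The documents do not show whether the counts or the error rates are the mistake. Confidence is high on the conflict, lower on which test would in fact be run.

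**What to change.** **8.4.3.1 and the CR row of Table 7.** Replace the pooled test with: *The composite CR rate (8.4.1) is tested one-sided in each HPV cohort, against 74% (HPV-positive) and 50% (HPV-negative), using the decision rule stated for that cohort in 8.4.7.3. The pooled CR rate is reported with a Clopper-Pearson 95% interval and is not tested.* State whether the count or a p-value decides, so that only one rule remains per cohort.

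**8.4.7.3.** The sponsor must choose one option and say so:
- keep 31/34 and 18/23, and restate alpha/power as 1.2%/55% and 0.5%/47%; or
- use 30/34 (3.8%/75%) and 16/23 (4.7%/80%), and disclose that this lowers the printed bar after 8/8 open-label HPV-positive CRs. With both nulls true, the chance of at least one false-positive cohort rises from 1 − (0.9878 × 0.9947) = 1.7% to 1 − (0.9625 × 0.9534) = 8.2%.

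**Other evaluable numbers.** Use the smallest count whose exact one-sided p is no larger than the alpha level the sponsor adopts. At 0.05 this gives 29/33 (alpha 4.5%, power 77%) and 16/22 (2.6%, 70%). If the printed counts are kept, levels of, for example, 0.02 (HPV-positive) and 0.01 (HPV-negative) reproduce 31/34 and 18/23 and give 30/33 (1.5%, 58%) and 17/22 (0.9%, 52%). Do not use the attained 0.0122 and 0.0053 as the levels: they give 31/33 and 18/22, with power of only 35% and 32%.

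**Consistency.** State the two cohort hypotheses in 8.1, change 39 to 34 + 23 in 8.4.7, align the endpoint in 8.4.7.1 and 8.4.7.3 with the composite CR, and label the 13/27 rule as part of the initial 40.2% design.

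**Cost.** Wording only, with no added patients or data. The bar is higher than the 40.2% test, and if the printed counts stay, the stated power falls from 80% to 55% and 47%.
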